Low Adherence (LA) Group: 14 days consisting of 3 pills/week (one tablet/dose) for a total of 6 pills ingested

High Adherence (HA) Group: 14 days consisting of 7 pills/week (one tablet/dose) for a total of 14 pills ingested

Criteria for evaluation:

Safety: It is expected that there will be no clinically significant concerns.

Statistical methods:

Sample size is based on feasibility rather than statistical considerations; thus, analysis will be primarily descriptive. Participant flowchart (e.g. number screened, number with sampling) will be provided.

The Full Analysis Set (FAS) will consist of all subjects who are randomized and have at least one post-baseline assessment.

All populations will be defined based on the adherence regimen.

Evaluation of Study Objectives: Study objectives will be evaluated by presentation of descriptive summaries and graphical displays.

Primary analysis of this study will evaluate the performance of the TFV aptasensor by comparing its measurements of the concentrations of TFV in clinical samples from all women with those values obtained from LC-MS/MS. Correlation and agreement between the TFV levels measured by the aptasensor and LC-MS/MS will be analyzed using scatterplot and linear regression. Continuous variables will be compared between values measured with the aptasensor versus LC-MS/MS using paired comparisons. From this comparison, sensitivity, specificity, NPV, and PPV of the aptasensor will also be determined. Confidence intervals will be calculated to assess precision and margin of error of those measures. Using the 14 baseline pre-dose samples, each woman will be her own control, and these pre-dose samples will be used for the assessment of specificity and NPV.

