5.2.1. Primary Objectives

- Compare plasma TFV concentrations measured by the aptasensor with those values quantitated by LC-MS/MS to determine agreement between the two methodologies, sensitivity, specificity, NPV, and PPV
- Determine if the TFV aptasensor can detect differences in the plasma TFV concentrations between high and low adherence dosing regimens and compare the mean difference to the difference calculated from values generated by LC-MS/MS

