7.2. Exclusion Criteria

Volunteers must not meet any of the following criteria prior to baseline sampling:

1. Currently pregnant
2. Currently breastfeeding or planning to breastfeed during the course of the study
3. In the last three months, diagnosed with or treated for any STI

4. Positive test for HIV, or Hepatitis B surface antigen (HBsAg)
5. Systemic use in the last two weeks or anticipated use during the study of any of the following: antiretrovirals (e.g. Viread®, Atripla®, Emtriva®, or Complera®), or drugs that may interact with TFV (e.g., protease inhibitors, anticonvulsants, antimycobacterials, St. John's Wort).
6. Participation in any other investigational trial with use of a drug/device within the last 30 days or planned participation in any other investigational trial with use of a drug/device during the study
7. Grade 2 or higher laboratory abnormality, per the 2014 update of the Division of AIDS, National Institute of Allergy and Infectious Disease (DAIDS) Table for Grading the Severity of Adverse Events, or clinically significant laboratory abnormality as determined by the clinician
8. Abnormal finding on laboratory or physical examination or a social or medical condition in the volunteer which, in the opinion of the investigator, would make participation in the study unsafe or would complicate interpretation of data

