8.2. Visit 2: Baseline Pre-Dose Sample Collection

This visit will be scheduled for the early follicular phase of the menstrual cycle (for cycling women).

- An interval history will be collected.
- Eligibility criteria will be reviewed. If any lab tests reveal that the participant is not eligible, the visit should not proceed and the participant will not continue in the study.
- If indicated by signs or symptoms or history, a directed physical exam and/or urine pregnancy test will be performed. If pregnancy is diagnosed, the participant will be referred as necessary and will be discontinued.

- A vaginal swab for prostate specific antigen (PSA) will be obtained, if the PSA test indicates semen exposure, the visit will be re-scheduled.
- A urine sample will be obtained.
- Vaginal swabs will be obtained
- A blood sample (approximately 2 teaspoons) will be obtained.
- The participant will be randomized to the HA versus LA regimen and will take her first doses of TDF/FTC in the clinic under direct observation and the time of product ingestion will be recorded in the source document. The pill will be ingested after urine, vaginal and blood samples are obtained.
- The participant will confirm her contact information for the medication text reminder.
- Participants will be instructed to refrain from vaginal intercourse for 48 hours prior to visits 3 – 5.

8.3. Visits 3 – 5: 24 hours , 7 days, and 14 days after first dose

Visits 3, 4, and 5 will be scheduled for 24 hours, 7 days, and 14 days after initial dosing at Visit 2, respectively. The time of the visit will assure that it has been at least 24 hours since the participant's last dose of TDF/FTC. At each visit, the following procedures will be performed:

- The study staff will ask the participant if she followed the instructions from the previous visit, and ask about adverse events and concomitant medications.
- If indicated, a directed physical exam, pelvic exam and/or pregnancy test will be performed. If pregnancy is diagnosed, the participant will be referred as necessary and will be discontinued.
- Visits 4 and 5: Study staff will count the number of pills remaining and query the participant on compliance with her assigned dosing regimen.
- A vaginal swab for PSA will be obtained, if the PSA test indicates semen exposure, the participant will be reminded of the restrictions on vaginal intercourse, but the visit will proceed.
- A urine sample will be obtained.
- Vaginal swabs will be obtained

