14.4. Statistical Analysis

Sample size is based on feasibility rather than statistical considerations; thus, analysis will be primarily descriptive. Participant flowchart (e.g. number screened, number with sampling) will be provided. All populations will be defined based on the adherence regimen.

Evaluation of Study Objectives: Study objectives will be evaluated by clinical review of descriptive summaries and graphical displays.

Primary analysis of this study will evaluate the performance of the TFV aptasensor by comparing its measurements of the concentrations of TFV in clinical samples from all women with those values obtained from LC-MS/MS. Correlation and agreement between the TFV levels measured by the aptasensor and LC-MS/MS will be analyzed using scatterplot and linear regression. Continuous variables will be compared between values measured with the aptasensor versus LC-MS/MS using paired comparisons. From this comparison, sensitivity, specificity, NPV, and PPV of the aptasensor will also be determined. Confidence intervals will be calculated to assess precision and margin of error of those

measures. Using the 14 baseline pre-dose samples, each woman will be her own control, and these pre-dose samples will be used for the assessment of specificity and NPV.

The secondary analysis of this study will evaluate whether the aptasensor can detect differences in TFV levels between the two independent cohorts of women taking TDF/FTC at different dosing regimens representing high (7 pills/week) and low adherence (3 pills/week). We will compare the two independent cohorts using an independent samples t test for normally distributed data or a Wilcoxon-Mann-Whitney test for non-parametric data. TFV concentrations from the LA and HA cohorts will be characterized using descriptive statistics (mean, median, interquartile range, minimum and maximum). The values will be compared between the high adherence and low adherence groups as well as comparing the mean difference between groups generated by the aptasensor to that difference generated by LC-MS/ MS. Distributions will be checked to determine normality so as to determine the appropriate statistical test.

Descriptive Statistics: Categorical variables will be summarized by frequencies and percentages. Continuous variables will be summarized by means, standard deviations, medians, quartiles, minima and maxima.

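### Section 14.4 ties NPV to the 14 pre-dose samples, where no false negative is expected, so NPV computed there is 100% whatever the aptasensor's sensitivity

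*Combined protocol and SAP*

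**What the plan says.** The first primary objective (Section 5.2.1) is to compare plasma tenofovir by aptasensor and LC-MS/MS "to determine agreement between the two methodologies, sensitivity, specificity, NPV, and PPV". Section 14.4 describes the primary analysis as "comparing its measurements of the concentrations of TFV in clinical samples from all women with those values obtained from LC-MS/MS", and continues: "From this comparison, sensitivity, specificity, NPV, and PPV of the aptasensor will also be determined". Confidence intervals are planned for these measures: "Confidence intervals will be calculated to assess precision and margin of error of those measures" (Synopsis, repeated in 14.4).

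The paragraph then turns to the 14 baseline pre-dose samples, saying that "each woman will be her own control, and these pre-dose samples will be used for the assessment of specificity and NPV". The Synopsis has the same rule: "these pre-dose samples will be used for the assessment of specificity and NPV". No other sentence says which samples serve NPV.

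Two further provisions fix what those samples contain. At Visit 2, "The pill will be ingested after urine, vaginal and blood samples are obtained" (Section 8.2). Section 7.2 excludes women with "Systemic use in the last two weeks or anticipated use during the study of any of the following: antiretrovirals".

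**The concern.** NPV is the proportion of sensor-negative samples that are truly negative. It can fall below 100% only if some reference-positive samples are among those tested. The baseline samples are expected to contain none, so an NPV taken from them says nothing about how often the sensor misses drug. It would still be reported, with a confidence interval, as a result for a primary objective of a proof-of-concept study whose statistics are meant to guide further development of the sensor.

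The text also does not say whether sensor-negative samples from Visits 3 to 5 are added to the baseline samples. No positivity cut-off is stated for either assay, so the 2x2 table behind all four measures is not yet defined. Specificity from the pre-dose samples is valid, though imprecise.

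**Working it through.** The documents give no expected NPV, accuracy target or confidence level, so there is no planned figure to reproduce.

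**Inputs from the documents**
- 14 women with one pre-dose sample each: 14 samples.
- Three post-dose visits (24 hours, 7 days, 14 days): 14 x 3 = 42 samples per fluid if complete, so 56 in all.

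**Assumptions, for illustration only**
- Sensitivity (Se) 80% or 90%; specificity (Sp) 13/14.
- Reference-positive share as shown in each case.
- 95% Clopper-Pearson intervals for single-sample proportions.

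**Step 1: NPV in the pre-dose samples alone**

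NPV = TN/(TN + FN). With no reference-positive sample, FN = 0, so NPV = TN/TN = 100% for every sensitivity from 0% to 100%. It is also 100% at almost any specificity:

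| Sensor-negative of 14 | Specificity | Pre-dose NPV | Exact 95% lower limit |
|---|---|---|---|
| 14 | 100% | 100% | 76.8% |
| 13 | 92.9% | 100% | 75.3% |
| 7 | 50% | 100% | 59.0% |
| 1 | 7.1% | 100% | 2.5% |

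The lower limit is 0.025^(1/TN). It follows the number of sensor-negative results, not the number of missed positives.

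One unexpected reference-positive sample among the 14 would change little. With Sp = 100%, expected NPV is 13/(13 + 0.5) = 96.3% at Se 50% and 13/(13 + 0.2) = 98.5% at Se 80%.

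**Step 2: NPV over all visits**

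NPV = Sp x neg / [Sp x neg + (1 - Se) x pos], with Sp = 13/14 applied to all reference-negative samples:

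| Reference-positive / negative | Se 80% | Se 90% |
|---|---|---|
| 42 / 14 | 13/(13 + 8.4) = 60.7% | 13/(13 + 4.2) = 75.6% |
| 35 / 21 | 19.5/(19.5 + 7) = 73.6% | 19.5/(19.5 + 3.5) = 84.8% |
| 28 / 28 | 26/(26 + 5.6) = 82.3% | 26/(26 + 2.8) = 90.3% |

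The lower rows allow for low-adherence samples below the LC-MS/MS limit. The last row takes all Visit 4 and 5 samples from 7 low-adherence women as negative (42 - 14 = 28 positive). Table 7 is only an example schedule, and the simple randomization in Section 9.4 does not guarantee 7 per arm.

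**Step 3: precision of the all-visit NPV**

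The 42/14 case was simulated with 200,000 runs of 14 women, each with one pre-dose and three reference-positive post-dose samples. Misses were beta-binomial within woman. Central 95% range of the estimate:

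| Within-woman correlation | Se 80% | Se 90% |
|---|---|---|
| 0 | 48% to 78% | 60% to 93% |
| 0.2 | 46% to 82% | 58% to 100% |

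**Step 4: specificity at baseline**

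14/14 gives an exact 95% CI of 76.8% to 100%; 13/14 gives 66.1% to 99.8%. These are wide but interpretable, with one sample per woman.

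**The case against.** The strongest reply is that the plan never says NPV is computed in the pre-dose samples alone. It first says that all four measures come from the comparison in samples from all women. The next sentence can then mean that baseline supplies the negative controls. On that reading the sentence is even true of an all-visit analysis: in the 42/14 case all 13 true negatives are pre-dose samples.

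That reading is open, but it does not remove the problem. The only sentence that matches samples to measures names the pre-dose samples for NPV, and no text brings false negatives from Visits 3 to 5 into the denominator. In the illustration the two readings give 100% and 61%. A plan that permits both for a primary-objective measure needs correcting.

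Other points stand in part:
- The contrast depends on assumed inputs. The pre-dose interval (75.3% to 100%) excludes 60.7%, but it just includes 75.6% and includes the 28/28 values. The 100% itself needs only FN = 0 and one sensor-negative result.
- An all-visit NPV has limited meaning too, because the visit schedule largely sets the positive share. At Se 90% and Sp 100%, NPV is 0.75/(0.75 + 0.025) = 96.8% at a 25% positive share and 0.25/(0.25 + 0.075) = 76.9% at 75%. The share must therefore be reported.
- The study is a feasibility-sized, descriptive pilot with no NPV threshold, and the sensitivity estimate would show missed samples. This limits the harm but does not make the NPV informative.
- The general objective in Section 5.2 includes vaginal fluid in the LC-MS/MS accuracy comparison, while Section 5.2.2 compares it with preclinical ranges. A rewrite limited to plasma and urine follows the specific objectives, and the sponsor should reconcile the two statements.

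**Conclusion.** The concern holds. As written, the rule assigns NPV to samples in which no false negative is expected, and NPV computed there is 100% regardless of sensitivity. This rests on the baseline samples being LC-MS/MS-negative, which the sampling order and exclusions make likely but do not guarantee, and on at least one of them reading negative.

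Under the stated assumptions an all-visit NPV would lie between about 61% and 90%. The gap from 100% is therefore about 10 to 39 percentage points, depending on sensitivity and the reference-positive share. The consequence is a misleading reported figure for a measure named in the first primary objective. No decision rule, sample size or power figure is affected. It should be fixed before analysis.

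**What to change.** In Section 14.4 and the Synopsis, remove NPV from the pre-dose sentence and keep those samples for a separately labelled baseline specificity. Then add text such as:

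*Sensitivity, specificity, PPV and NPV are computed from one 2x2 table of all paired aptasensor and LC-MS/MS samples across visits, separately for plasma and for urine, with LC-MS/MS as the reference. The positivity cut-off for each assay is fixed before any paired aptasensor and LC-MS/MS results are compared.*

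In addition:
- The cut-offs are the sponsor's choice. They need locking before the paired comparison because the laboratory and analyst blinding in Section 9.4 covers study treatment only.
- Report the observed share of reference-positive samples, and state that PPV and NPV depend on it. Base any PPV or NPV at other prevalences on the sensitivity and specificity from the same table, not on baseline specificity.
- Use exact intervals for baseline specificity (one sample per woman) and woman-clustered intervals for the all-visit measures (up to four samples per woman).

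The cost is protocol and SAP wording, with no new samples or visits. If a pre-dose-only NPV was intended and any post-dose sample is missed, the reported NPV will be lower. Its interval from 14 women will be wide, roughly 46% to 82% in the 42/14 illustration with sensitivity 80% and correlation 0.2.

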14.5. Interim Analysis

No interim analysis will be conducted.

15. MANAGEMENT OF INTERCURRENT EVENTS

15.1. Loss to Follow-up

If a participant fails to appear for a scheduled visit, at least three attempts to contact her should be made over the subsequent 30 days. These attempts should be documented in the participant's study file. The final attempt must be a certified letter to the participant with return-receipt requested, or an outreach attempt. A copy of this letter or documentation of the final outreach attempt should be in her file. After these three attempts, no further efforts need to be made to find her, but her file should remain open until study closeout.

If the participant does not contact the clinic before the study is closed, her final disposition will be recorded at the time of study closeout, to indicate that she was lost to follow-up. The lost to follow-up designation cannot be made for any participant until study close out.

15.2. Protocol Adherence and Sampling Windows

Visits 3, 4 and 5 should be scheduled so that it has been at least 24 hours since the participant's last dose of study medication. Visit 3 should be conducted 24 hours + 4 hours from the ingestion of the first dose at Visit 2. Visit 4 should be conducted 7 days + 6 hours from the ingestion of the first dose at visit 2. Visit 5 should be conducted 14 days + 6 hours from the ingestion of the first dose at visit 2.

The study site should carefully record the date and time of each collection of blood, urine and CV swabs. The site should carefully record the date and time of each ingestion of medication in the clinic.

15.3. Protocol Violations

If a protocol violation is required to protect the life or physical well-being of a participant in an emergency, it may be carried out without prior approval from the IRB. The investigator must, however, report the violation to the IRB as soon as possible, no later than 5 working days after the emergency occurred.

Other violations from the protocol may not be carried out without prior approval from the IRB if the change involves the rights, safety, or welfare of participants; and without prior approval from the grant PI ([name]) if the change involves the validity of the data, the study's scientific soundness or the rights, safety, or welfare of participants.

All protocol violations should be recorded in a protocol violation log.

15.4. Modification of Protocol

No modification of this protocol may be made without written approval of [name].

16. DIRECT ACCESS TO SOURCE DATA/DOCUMENTS

16.1. Study Monitoring

The study site may be monitored by the EVMS IRB at any time. This monitoring may include:

- Confirm that facilities remain acceptable
- Confirm that the investigational team is adhering to the protocol, that data are being accurately recorded in the CRFs, and that investigational product accountability checks are being performed
- Confirm all volunteers have been properly consented
- Record and report any protocol violations not previously sent to the IRB
- Confirm AEs and SAEs have been properly documented and confirm any SAEs have been forwarded to the IRB and those SAEs that met criteria for reporting have been forwarded to the IRB

16.2. Institutional Review Board (IRB)

The Principal Investigator (PI) must obtain IRB approval for the investigation. Initial IRB approval, and all materials approved by the IRB for this study including the patient consent form and recruitment materials must be maintained by the Investigator and made available for inspection.

17. ETHICS

17.1. Ethics Review

The final study protocol, including the final version of the informed consent form, must be approved or given a favorable opinion in writing by an IRB or IEC as appropriate. The study must be conducted in accordance with all conditions of approval by the IRB.

The PI is responsible for informing the IRB or IEC of any amendment to the protocol in accordance with local requirements. In addition, the IRB or IEC must approve all advertising used to recruit patients for the study. The protocol must be re-approved by the IRB or IEC upon receipt of amendments and annually, as local regulations require.

17.2. Ethical Conduct of the Study

The study will be performed in accordance with ethical principles that have their origin in the Declaration of Helsinki and are consistent with ICH GCP, and applicable regulatory requirements. In addition, the PI will follow U.S. Department of Health and Human Services regulations regarding the Health Information Portability and Accountability Act (HIPAA 45, CFR 164). The PI will ensure that appropriate health care or referral is provided for the participants throughout the study.

17.3. Written Informed Consent

17.3.1. Procedure for Obtaining Informed Consent

No volunteer may be admitted into this study until the PI (or designee) has obtained her legally effective informed consent. The PI (or designee) shall seek such consent only under circumstances that provide the prospective participant with sufficient opportunity to consider whether or not to participate in the study. Informed consent must be obtained without coercion, undue influence, or misrepresentation of the potential benefits or risks that might be associated with participation in the study.

Informed consent encompasses all oral and written information given to the volunteer about the study and the study materials. This includes the consent form signed by the participant, the instructions for use of study materials that are provided to the participant, recruitment advertising, and any other information provided to the participant. All such information that is given to the participant will be in a language that is understandable to her. The information will not include any language in which the participant is made to waive any of her rights or which releases or appears to release the PI or the PI's institution from liability for negligence.

Informed consent will be documented by the use of a written consent form that is signed by the participant and the PI (or designee). A copy of the consent form will be offered to each participant. The original signed consent form for each participant will be kept at the site. The consent form must include each of the basic and additional elements of informed consent described in 21 CFR Part 50.25 and must describe each of the risks or discomforts to the participant that have been identified as reasonably foreseeable.

